**The next questions are about how you feel and how things have been with you during the past four weeks.**

**As I read each statement, please give me the one answer that comes closest to the way you have been feeling; is it all of the time, most of the time, some of the time, a little of the time, or none of the time?**

9a. **How much of the time during the past four weeks . . . did you feel full of life?**  
*[READ RESPONSE CHOICES]*

*(Circle one number)*

- All of the time..... 1
- Most of the time ..... 2
- Some of the time ..... 3
- A little of the time ..... 4
- or None of the time..... 5

9b. **How much of the time during the past four weeks . . . have you been very nervous?** *[READ RESPONSE CHOICES]*

*(Circle one number)*

- All of the time..... 1
- Most of the time ..... 2
- Some of the time ..... 3
- A little of the time ..... 4
- or None of the time..... 5

9c. **How much of the time during the past four weeks . . . have you felt so down in the dumps that nothing could cheer you up?** *[READ RESPONSE CHOICES ONLY IF NECESSARY]*

*(Circle one number)*

- All of the time..... 1
- Most of the time ..... 2
- Some of the time ..... 3
- A little of the time ..... 4
- or* None of the time..... 5

9d. **How much of the time during the past four weeks . . . have you felt calm and peaceful?** *[READ RESPONSE CHOICES ONLY IF NECESSARY]*

*(Circle one number)*

- All of the time..... 1
- Most of the time ..... 2
- Some of the time ..... 3
- A little of the time ..... 4
- or* None of the time..... 5

9e. **How much of the time during the past four weeks . . . did you have a lot of energy?** *[READ RESPONSE CHOICES ONLY IF NECESSARY]*

*(Circle one number)*

- All of the time..... 1
- Most of the time ..... 2
- Some of the time ..... 3
- A little of the time ..... 4
- or* None of the time..... 5

9f. **How much of the time during the past four weeks . . . have you felt downhearted and depressed?** *[READ RESPONSE CHOICES ONLY IF NECESSARY]*

*(Circle one number)*

- All of the time..... 1
- Most of the time ..... 2
- Some of the time ..... 3
- A little of the time ..... 4
- or* None of the time..... 5

- 9g. **How much of the time during the past four weeks . . . did you feel worn out?**  
*[READ RESPONSE CHOICES ONLY IF NECESSARY]*  
*(Circle one number)*
- All of the time..... 1  
Most of the time ..... 2  
Some of the time ..... 3  
A little of the time ..... 4  
or None of the time..... 5
- 9h. **How much of the time during the past four weeks . . . have you been happy?**  
*[READ RESPONSE CHOICES ONLY IF NECESSARY]*  
*(Circle one number)*
- All of the time..... 1  
Most of the time ..... 2  
Some of the time ..... 3  
A little of the time ..... 4  
or None of the time..... 5
- 9i. **How much of the time during the past four weeks . . . did you feel tired?** *[READ RESPONSE CHOICES ONLY IF NECESSARY]*  
*(Circle one number)*
- All of the time..... 1  
Most of the time ..... 2  
Some of the time ..... 3  
A little of the time ..... 4  
or None of the time..... 5
10. **During the past four weeks, how much of the time has your physical health or emotional problems interfered with your social activities like visiting with friends or relatives? Has it interfered . . .** *[READ RESPONSE CHOICES]*  
*(Circle one number)*
- All of the time..... 1  
Most of the time ..... 2  
Some of the time ..... 3  
A little of the time ..... 4  
or None of the time..... 5

**These next questions are about your health and health-related matters.**

**Now, I'm going to read a list of statements. After each one, please tell me if it is definitely true, mostly true, mostly false, or definitely false. If you don't know, just tell me.**

11a. **I seem to get sick a little easier than other people. Would you say that's . . .** [READ RESPONSE CHOICES]

*(Circle one number)*

- Definitely true..... 1
- Mostly true ..... 2
- Don't know ..... 3
- Mostly false ..... 4
- or Definitely false..... 5

11b. **I am as healthy as anybody I know. Would you say that's . . .** [READ RESPONSE CHOICES]

*(Circle one number)*

- Definitely true..... 1
- Mostly true ..... 2
- Don't know ..... 3
- Mostly false ..... 4
- or Definitely false..... 5

11c. **I expect my health to get worse. Would you say that's . . .** [READ RESPONSE CHOICES]

*(Circle one number)*

- Definitely true..... 1
- Mostly true ..... 2
- Don't know ..... 3
- Mostly false ..... 4
- or Definitely false..... 5

11d. **My health is excellent. Would you say that's . . .** [READ RESPONSE CHOICES]

*(Circle one number)*

- Definitely true..... 1
- Mostly true ..... 2
- Don't know ..... 3
- Mostly false ..... 4
- or Definitely false..... 5

**DO NOT read the following text to the survey respondent**

**Important Instruction for Interviewer:**

When using this script for interview administration of the SF-36v2 survey, note that items 7 and 8 from the Bodily Pain health domain scale are administered in reverse order from the way they appear on the printed SF-36v2 self-administered paper form. Reversing the order of the presentation of these two items facilitates the flow of the interview administration.

When recording responses from interview administration of the SF-36v2, the response to Item 7 from the interview script should be entered in the Item 8 response area on the paper form, and vice versa.

Note: All QualityMetric scoring solutions only support the scoring of items as ordered on the printed SF-36v2 self-administered paper form.

## Appendix 8 - EQ-5D Health Questionnaire

Health Questionnaire

English version for the UK

*UK (English) v.2 © 2009 EuroQol Group. EQ-5D™ is a trade mark of the EuroQol Group*

Under each heading, please tick the ONE box that best describes your health TODAY

**MOBILITY**

- I have no problems in walking about
- I have slight problems in walking about
- I have moderate problems in walking about
- I have severe problems in walking about
- I am unable to walk about

**SELF-CARE**

- I have no problems washing or dressing myself
- I have slight problems washing or dressing myself
- I have moderate problems washing or dressing myself
- I have severe problems washing or dressing myself
- I am unable to wash or dress myself

**USUAL ACTIVITIES** (e.g. work, study, housework, family or leisure activities)

- I have no problems doing my usual activities
- I have slight problems doing my usual activities
- I have moderate problems doing my usual activities
- I have severe problems doing my usual activities
- I am unable to do my usual activities

**PAIN / DISCOMFORT**

- I have no pain or discomfort
- I have slight pain or discomfort
- I have moderate pain or discomfort
- I have severe pain or discomfort
- I have extreme pain or discomfort

[figure not shown]
**ANXIETY / DEPRESSION**

- I am not anxious or depressed
- I am slightly anxious or depressed
- I am moderately anxious or depressed
- I am severely anxious or depressed
- I am extremely anxious or depressed

- We would like to know how good or bad your health is TODAY.
- This scale is numbered from 0 to 100.
- 100 means the best health you can imagine.  
0 means the worst health you can imagine.
- Mark an X on the scale to indicate how your health is TODAY.
- Now, please write the number you marked on the scale in the box below.

YOUR HEALTH TODAY =

The best health  
you can imagine

The worst health  
you can imagine

## Appendix 9 - Labelling of IMP and Rescue Medication

### **EU Primary (Blister) label (version number: DIUR-005.IMP.EU.01.001)**

#### **Chronocort® Hydrocortisone Modified Release Capsules X mg**

Sponsor: Diurnal Ltd., Cardiff, U.K. [contact]

PI: [REDACTED]

CRO: [REDACTED]

[REDACTED]

Dose instruction: The morning dose of Chronocort® should be taken on an empty stomach at least 1 hour before a meal and the evening dose should be taken at least 2 hours after the last meal of the day

Batch No.: XXXX

Protocol No.: DIUR-005

Subject No.: YY

EudraCT-No. 2015-000711-40

Keep out of reach of children

### **EU Secondary (Blister) label (version number: DIUR-005.IMP.EU.02.001)**

#### **Chronocort® Hydrocortisone Modified Release Capsules X mg**

Quantity: 100 capsules

Batch No.: XXXX

Storage: Store at no more than 25°C

Expiry: MM/YYYY

Protocol No.: DIUR-005

Subject No.: YY

Pack No.: YY

Directions for use: For oral administration. The morning dose of Chronocort® should be taken on an empty stomach at least 1 hour before a meal and the evening dose should be taken at least 2 hours after the last meal of the day

For clinical trial use only

Investigator: [REDACTED]

Sponsor: Diurnal Ltd., Cardiff, U.K. [contact]

CRO: [REDACTED]

[REDACTED]

EudraCT-No. 2015-000711-40

No special precautions for unused product: refer to accompanying documents

Keep out of reach of children

### **EU Primary (Bottle) label (version number: DIUR-005.IMPBOT.EU.01.001)**

#### **Chronocort® Hydrocortisone Modified Release Capsules X mg**

Quantity: 100 capsules

Batch No.: XXXX

Storage: Store at no more than 25 °C

Expiry: MM/YYYY

Protocol No.: DIUR-005

Subject No.: YY

Pack No.: YY

Directions for use: For oral administration. The morning dose of Chronocort® should be taken on an empty stomach at least 1 hour before a meal and the evening dose should be taken at least 2 hours after the last meal of the day

For clinical trial use only

Investigator: [REDACTED]

Sponsor: Diurnal Ltd., [name], U.K. [contact]

CRO: [REDACTED]

EudraCT-No. 2015-000711-40

No special precautions for unused product: refer to accompanying documents

Keep out of reach of children

**EU comparator label (version number: DIUR-005.COMP.EU.02.001)**

Protocol No.: DIUR-005

Subject No.: YY

Sponsor: Diurnal Ltd., Cardiff, U.K. [contact]

PI: [REDACTED]

EudraCT-No. 2015-000711-40

**EU safety pack label (version number: DIUR-005.SAFE.EU.02.001)**

Protocol No.: DIUR-005

Subject No.: YY

Contents: YY

Sponsor: Diurnal Ltd., Cardiff, U.K. [contact]

PI: [REDACTED]

EudraCT-No. 2015-000711-40

**US Primary (Blister) label (version number: DIUR-005.IMP.US.01.001)**

**Chronocort® Hydrocortisone Modified Release Capsules X mg**

Sponsor: Diurnal Ltd., Cardiff, U.K. [contact]

PI: [REDACTED]

CRO: [REDACTED]

Dose instruction: The morning dose of Chronocort® should be taken on an empty stomach at least 1 hour before a meal and the evening dose should be taken at least 2 hours after the last meal of the day

Batch No.: XXXX

Protocol No.: DIUR-005

Subject No.: YY

IND No.: 076485

Keep out of reach of children

CAUTION: New Drug Limited by Federal (or United States Law) for Investigational Use

**US Secondary (Blister) label (version number: DIUR-005.IMP.US.02.001)**

**Chronocort® Hydrocortisone Modified Release Capsules X mg**

Quantity: 100 capsules

Batch No.: XXXX

Storage: Store at no more than 25°C

Expiry: MM/YYYY

Protocol No.: DIUR-005

Subject No.: YY

Pack No.: YY

IND No.: 076485

Directions for use: For oral administration. The morning dose of Chronocort® should be taken on an empty stomach at least 1 hour before a meal and the evening dose should be taken at least 2 hours after the last meal of the day

Investigator: [REDACTED]

Sponsor: Diurnal Ltd., Cardiff, U.K. [contact]

CRO: [REDACTED]

[REDACTED]

No special precautions for unused product: refer to accompanying documents

Keep out of reach of children

CAUTION: New Drug Limited by Federal (or United States Law) for Investigational Use

**US Primary (Bottle) label (version number: DIUR-005.IMPBOT.US.01.001)**

**Chronocort® Hydrocortisone Modified Release Capsules Xmg**

Quantity: 100 capsules

Batch No.: XXXX

Storage: Store at no more than 25°C

Expiry: MM/YYYY

Protocol No.: DIUR-005

Subject No.: YY

Pack No.: YY

Directions for use: For oral administration. The morning dose of Chronocort® should be taken on an empty stomach at least 1 hour before a meal and the evening dose should be taken at least 2 hours after the last meal of the day

Keep out of reach of children

No special precautions for unused product: refer to accompanying documents

CAUTION: New Drug Limited by Federal (or United States Law) for Investigational Use

IND No.: 076485

Sponsor: Diurnal Ltd., [name], U.K. [contact]

PI: [REDACTED]

CRO: [REDACTED]

[REDACTED]

**US comparator label (version number: DIUR-005.COMP.US.02.001)**

Protocol No.: DIUR-005

Subject No.: YY

Sponsor: Diurnal Ltd., Cardiff, U.K. [contact]

PI: [REDACTED]

IND No.: 076485

**US safety pack label (version number: DIUR-005.SAFE.US.02.001)**

Protocol No.: DIUR-005

Subject No.: YY

Contents: YY

Sponsor: Diurnal Ltd., Cardiff, U.K. [contact]

PI: [REDACTED]

IND No.: 076485

## Appendix 10 - Protocol Amendment History

### Protocol Version 1.0 dated 03 July 2015

Original protocol.

### Protocol Version 2.0 dated 03 September 2015

The protocol was amended to address MHRA comments on the protocol and to make a small administrative change to the Adrenal Insufficiency Checklist. The following changes were made:

- 1) Modification of the RSI in the Investigator's Brochure (IB) necessitated an update to Appendix 3 (Expected Adverse Events) in the protocol.
- 2) Clarification was added that the DSMB is independent.
- 3) The inclusion criteria of PRA less than 2 x ULN was reduced to PRA less than 1.5 x ULN.
- 4) Appendix 5 was updated to a newer version of the Adrenal Insufficiency Checklist (minor administrative change).

### Protocol Version 3.0 dated 03 December 2015

The protocol was amended to address the Swedish Medicines Agency and the US National Institutes of Health comments on the protocol that a separate benefit/risk assessment should be added. The following changes were made:

- 1) Section 5: new section added at the end of Section 5 titled Benefit/Risk Assessment.

### Protocol Version 4.0 dated 28 May 2016

The following changes were made to the protocol:

- 1) The Sponsor signatory was changed from [REDACTED].
- 2) Different clinicians use different conversion factors for dexamethasone to hydrocortisone. The protocol states that 'The initial dose setting at the start of Chronocort® treatment will be made on hydrocortisone dose equivalent of baseline therapy, with the hydrocortisone dose calculated as dexamethasone dose multiplied by 80'. Investigators and Diurnal have been concerned that this may lead to a safety issue that if patients on a higher dose of dexamethasone were converted by x80 they would be exposed to excess hydrocortisone, therefore a greater mineralocorticoid effect, and be at risk of being overdosed. Therefore the protocol was amended to state that the current conversion rate of x80 should be used as per protocol up to a maximum starting dose of Chronocort® 30mg (split 20mg at night and 10mg in the morning). The justification for the maximum of 30mg Chronocort® is based on the fact this was the starting dose for all patients in the Phase 2 study (DIUR-003) (Mallappa 2015) and is in line with recommendations for hydrocortisone dosing in CAH (Speiser 2010). If the investigator has any concerns regarding the starting dose in a patient then these can be discussed with the Medical Monitor.
- 3) The protocol stated that blood samples should be taken for genotyping, unless genotyping had previously been performed. It was clarified that if previous genotyping had been performed the patient has to be asked for their permission for this information to be taken from their medical records.

- 4) Subjects who routinely work night shifts and so do not sleep during the usual nighttime hours was added to the exclusion criteria.
- 5) At the request of the Dutch ethics committee, the following sentence has been added to the procedures for the screening visit (Section 11.1.1) and also in Section 11.4 (Informed Consent): At Dutch centres only, potential subjects will be approached by their own treating physician. If the treating physician is also the investigator the subject information sheet can be provided immediately. If this is not the case then the treating physician will ask the patient for permission for the investigator to approach them about study participation.
- 6) It was noted that the terminology for the independent blinded physician was not consistent throughout the protocol so this was corrected throughout.
- 7) In the synopsis, Section 8 (Study Design) and Section 10.4 (Dose Adjustment) it was stated that ‘Dose adjustment will not take place without measurement of androgens at an inpatient visit, unless the local investigator considers it is indicated by the severity of symptoms.’ However, this statement was considered confusing and also seemed to mandate the measurement of androgens at an unscheduled dose adjustment, which was not the case. The text was therefore revised to say ‘No dose adjustments outside of the protocol-defined dose adjustments should be conducted, unless clinical signs and symptoms indicate an immediate need. In such cases the Sponsor’s medical monitor must be contacted (preferably before any dose changes are implemented). Any such unscheduled dose adjustments should be based on clinical symptoms only, with repeated androgen testing discouraged and must be pre-approved by the Sponsor’s medical monitor.’

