This physiological replacement of cortisol with Chronocort® improved the control of disease-related biomarker androgens in subjects (control compared to baseline standard therapy). This was achieved with a similar dose of glucocorticoid; the mean hydrocortisone dose equivalent on standard therapy was 28mg and on Chronocort® was 26mg. On standard therapy at baseline, the majority of subjects had uncontrolled androgen levels, with most having high levels of 17-OHP and A4. Following 6-months titration with Chronocort®, the majority of subjects had 17-OHP and A4 levels in the normal or optimal range (see Figure 1).

**Figure 1: 17-OHP levels (mean  $\pm$  standard error of the mean) during standard therapy at baseline and after the first administration of Chronocort® (Day 1) and following 6 months of continued Chronocort® treatment**

There were no safety issues reported in DIUR-002. There were no serious adverse events (SAEs) and no events leading to withdrawal from study DIUR-003. Two groups of adverse events (AEs) were considered sufficiently remarkable to warrant examination at the time: 5 cases of anaemia and 4 cases of median nerve entrapment (carpal tunnel) syndrome. The anaemia cases were all consistent with acute low level red cell reduction attributable to blood loss secondary to the blood draws related to the study. The aetiology of the carpal tunnel syndrome was not clear, although thought most likely to be due to increased fluid retention. All events were mild and their relationship to the investigational medicinal product (IMP) was uncertain. All subjects recovered and the findings were not considered to alter the risk/benefit analysis or to raise cause for concern.

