## **Baseline Assessment and Randomisation (2-day visit)**

Subjects will be called in for the Baseline Visit (Visit 1) and admitted overnight for a 24-hour endocrine profile whilst remaining on their standard therapy. Subjects will have 17-OHP and A4 measured at 13 time points. On the second morning baseline bloods will be taken together with all safety measures and all secondary endpoint measurements (see Section 11).

After the completion of the baseline profile, the subject will be randomised either to receive Chronocort® or to continue on standard care. 120 subjects will be randomised (see Section 11).

The initial dose setting at the start of Chronocort® treatment will be made on hydrocortisone dose equivalent of baseline therapy, with the hydrocortisone dose calculated as prednisone dose multiplied by 5 and dexamethasone dose multiplied by 80 (up to a maximum starting dose of Chronocort® 30mg, split as 20mg at night and 10mg in the morning) Chronocort® will be given at 23:00 hours (approximately 2/3rd of the total daily dose) and 07:00 hours (approximately 1/3rd of the total daily dose). The first dose of Chronocort® will be taken at 23:00 hours on Day 2 of the baseline visit. Subjects will be asked to write on the pack the dose, date and time they took the first dose of study medication (Chronocort® or standard therapy).

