### ***13.1 Conventions and Methods***

#### ***13.1.1 Summary Tables, Listings and Figures***

The standard summary statistics for continuous baseline and outcome variables are: N, mean, standard deviation (SD), median, quartiles, minimum and maximum. The standard summary statistics for categorical baseline and outcome variables are: count and proportion (expressed as percentage). Geometric mean and coefficient of variation will also be presented for variables which will subsequently be log-transformed during the analysis.

All efficacy variables, vital signs and laboratory assessments, together with their changes from baseline, will be summarised by treatment group (Chronocort®, standard therapy), stratum

(previous stable therapy: hydrocortisone only, prednisone or prednisolone with hydrocortisone [but not dexamethasone], dexamethasone alone or in combination with either prednisolone, prednisone or hydrocortisone) and timepoint.

Baseline and demographic data will be summarised by treatment group and stratum. Shift tables from baseline will be provided for vital signs and laboratory assessments.

Data on dose changes indicated by the independent blinded physician, non-implemented changes and reasons for non-implementation will be presented descriptively by treatment group.

Where appropriate, graphical displays of variables assessed serially over time may be presented.

The summary tables and figures will be supported by full subject listings.

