### 9.2.3. Conversion factors

For the conversion of standard glucocorticoid replacement therapy to hydrocortisone, the conversion factors (Finkelstein 2012) are given in Table 4.

*Table 4: Conversion factors for standard glucocorticoid replacement therapy to hydrocortisone*

Standard glucocorticoid replacement therapy	Conversion factor
Prednisone or prednisolone	5
Dexamethasone	80 (up to a maximum starting dose of Chronocort® 30mg, split as 20mg at night and 10mg in the morning)

*Note: The conversion factor for Chronocort® is 1.*

For example, if a subject was previously taking 6mg daily of prednisone daily, this would be multiplied by a conversion factor of five and the equivalent hydrocortisone daily dose would be 30mg.

If a subject was previously taking prednisone in combination with hydrocortisone, then a conversion factor of five would be applied to the prednisone component of the dose, and a conversion factor of one would be applied to the hydrocortisone component of the dose, and the two added together.

All laboratory results will be reported in SI and conventional units. If for any reason the results are not collected in SI or conventional units, a conversion will be performed. Examples of some conversions to SI units are given in Table 5.

*Table 5: SI unit conversions*

Quantity	Conversion to SI units		
17-OHP	1 ng/dL	= 0.0303	nmol/L
ACTH	1 pg/mL	= 0.22	pmol/L
Androstenedione	1 ng/dL	= 0.0349	nmol/L
Glucose	1 mg/dL	= 0.0555	mmol/L
Insulin	1 µIU/mL	= 6.945	pmol/L
Osteocalcin	1 µg/L	= 0.171	nmol/L
PRA	1 NG/ML/HR	= 0.2778	NG/L/S

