#### 10.7.4. Use of glucocorticoids

Use of glucocorticoids at visit 1 (baseline) and visit 4 (week 24) of the study will be presented as individual glucocorticoids used. Change in dose of last glucocorticoid from baseline to each visit will be presented as hydrocortisone equivalents using accepted conversion constants for the calculations (see Section 9.2.3).

A summary of the frequency and percent of subjects with total hydrocortisone dose equivalent increments versus baseline at each visit falling within the following categories:

- Dose increases versus baseline:
  - No increase observed ( $\leq 0$ mg),
  - $> 0$  to  $\leq 5$ mg increase,
  - $> 5$  to  $\leq 10$ mg increase,
  - $> 10$  to  $\leq 15$ mg increase,
  - $> 15$  to  $\leq 20$  mg increase,
  - $> 20$  to  $\leq 25$  mg increase,
  - $> 25$  to  $\leq 30$  mg increase and
  - $> 30$  mg increase.
- Dose decreases versus baseline:
  - No decrease observed ( $\leq 0$ mg),
  - $> 0$  to  $\leq 5$ mg decrease,
  - $> 5$  to  $\leq 10$ mg decrease
  - $> 10$  to  $\leq 15$ mg decrease,
  - $> 15$  to  $\leq 20$  mg decrease,
  - $> 20$  to  $\leq 25$  mg decrease,
  - $> 25$  to  $\leq 30$  mg decrease and
  - $> 30$  mg decrease.

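### The hydrocortisone-equivalent dose summary rests on one dexamethasone factor that does not cancel in the Chronocort arm, and no planned analysis varies it or requires the dose tables by stratum

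*Protocol*

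**What the plan says.** Protocol 7.3 lists glucocorticoid use at the beginning and end of the study as an exploratory endpoint, shown both as individual drugs and as hydrocortisone equivalents. The SAP carries this out in 10.7.4: "Change in dose of last glucocorticoid from baseline to each visit will be presented as hydrocortisone equivalents using accepted conversion constants for the calculations". It adds a table of increases and decreases in mg bands.

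The constants are in SAP 9.2.3, Table 4. Prednisone and prednisolone are converted at 5. The dexamethasone entry reads "80 (up to a maximum starting dose of Chronocort® 30mg, split as 20mg at night and 10mg in the morning". A note under the table adds: "The conversion factor for Chronocort® is 1". Protocol section 8 uses the same constants to set the Chronocort starting dose ("prednisone dose multiplied by 5 and dexamethasone dose multiplied by 80"), with the same 30 mg cap.

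Protocol Appendix 10, version 4.0, gives the reason for the cap. It says "Different clinicians use different conversion factors for dexamethasone to hydrocortisone", and records concern about converting higher dexamethasone doses at 80. The factor was kept and the starting dose was capped.

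On strata, Protocol 13.1.1 states that efficacy variables and their changes from baseline "will be summarised by treatment group (Chronocort®, standard therapy), stratum" and timepoint. Protocol 13.3.4 lists glucocorticoid use among the exploratory efficacy variables. SAP 10.7.4 and the dose tables in SAP 14.1 name no stratum, and SAP section 12 declares no change on this point.

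**The concern.** Control subjects keep the same drugs throughout (Protocol section 8, Dose Adjustment), so baseline and follow-up are multiplied by the same constant. Subjects switched to Chronocort have their baseline multiplied by the constant and their follow-up by 1. The constant therefore acts differently in the two arms.

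The protocol acknowledges that clinicians do not agree on the dexamethasone constant, yet no analysis varies it: the only sensitivity analysis specified in SAP 10.7.5 concerns the definition of the SDS. Protocol section 8 describes the phase II result as better androgen control without increased glucocorticoid exposure, and section 5 gives the doses behind that: "the mean hydrocortisone dose equivalent on standard therapy was 28mg and on Chronocort® was 26mg". If a similar statement is made for this trial from a table not split by stratum, part of the apparent dose difference could come from the constant.

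**Working it through.** **Inputs from the documents.** Factors: dexamethasone 80, prednisone/prednisolone 5, Chronocort 1 (SAP Table 4). Starting cap 30 mg (Protocol section 8). Usual dexamethasone titration step 0.25 mg (Protocol section 8, Dose Adjustment). Phase II mean doses 28 and 26 mg (Protocol section 5).

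**Assumptions.** Dexamethasone doses of 0.25, 0.375 and 0.5 mg/day; alternative dexamethasone factors of 60, 50 and 40; an alternative prednisone factor of 4; dexamethasone shares of 10% and 20%. The documents give none of these. All figures use total daily dose and, except in step 5, an uncapped baseline equivalent.

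**The plan's own example.** 6 mg prednisone x 5 = 30 mg, as SAP 9.2.3 states.

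**1. Chronocort arm.** Change = C - f x D0, where C is the Chronocort dose, D0 the baseline dexamethasone dose and f the factor. The sign turns at f = C / D0.

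- D0 = 0.5 mg, C = 30 mg (the cap): 30 - 80 x 0.5 = -10 mg; 30 - 60 x 0.5 = 0; 30 - 50 x 0.5 = +5 mg. The sign turns at 30 / 0.5 = 60. The same subject falls in three different results of the SAP 10.7.4 banding: a decrease of over 5 and up to 10 mg, no change, and an increase of up to 5 mg.
- D0 = 0.25 mg, C = 80 x 0.25 = 20 mg (below the cap, before titration): 20 - 20 = 0 at 80, and 20 - 60 x 0.25 = +5 mg at 60. The zero at 80 arises by construction, because that factor set the dose.

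**2. Control arm.** Change = f x (D24 - D0). It is zero at any f if the dose is unchanged. One 0.25 mg step scores 80 x 0.25 = 20 mg, or 60 x 0.25 = 15 mg. For dexamethasone alone the direction is fixed and the size scales with f. In a mixed regimen the direction can turn: +10 mg hydrocortisone with -0.25 mg dexamethasone gives 10 - 0.25f, which is zero at f = 40.

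**3. Between arms.** With balanced baselines, the difference in mean change moves by -w x D24 mg per unit of f, where w is the share of subjects on dexamethasone and D24 their mean control dose at week 24. Taking D24 = 0.375 mg:

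- 80 to 60: 0.10 x 0.375 x 20 = 0.75 mg at a 10% share; 1.5 mg at 20%.
- 80 to 40: 0.10 x 0.375 x 40 = 1.5 mg at 10%; 3.0 mg at 20%.

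For scale only, take a baseline of 28 mg (scored at 80) and 26 mg on Chronocort, with dexamethasone supplying a fraction s of the baseline equivalents. Change = 26 - 28 x [(1 - s) + s x f/80].

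- s = 0.10: -1.30 mg at 60 and -0.60 mg at 40. No sign change.
- s = 0.20: -0.60 mg at 60 and +0.80 mg at 40.
- The sign turns only if s is at least (2/28) / (1 - f/80), which is 0.29 at 60 and 0.14 at 40.

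**4. Prednisone and prednisolone.** A subject on 6 mg prednisone moved to 30 mg Chronocort shows 30 - 5 x 6 = 0 at 5, and 30 - 4 x 6 = +6 mg at 4. The structure is the same.

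**5. The cap inside Table 4.** For 0.5 mg dexamethasone and 26 mg Chronocort, the uncapped baseline is 40 mg and the change is 26 - 40 = -14 mg. If the cap applies to the baseline equivalent, the change is 26 - 30 = -4 mg. Table 4 does not say which is meant. The factor matters even under the capped reading: at 50 the baseline is 25 mg and the change is +1 mg.

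**The case against.** The endpoint is exploratory and the SAP describes no test for it. No stated objective claims dose neutrality, and the individual drugs are also shown unconverted. The factor is prespecified, has a cited source and matches the one used for dosing. All of this stands, and it keeps the point minor. Matching the dosing factor does not help the analysis, though: as step 1 shows, it makes the early change zero by construction for subjects below the cap.

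The -10 mg example describes the dose before any titration and does not predict week 24. That also stands; it shows the mechanism only.

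A reader might infer that the constant simply cancels in the control arm. It does so only for an unchanged dose, and control doses may be titrated. A reader might also infer that the protocol regards 80 as wrong or contested. It does not: it reports differing practice and a concern about starting doses, and it retains 80.

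On strata, the SAP's silence is not a decision to pool. Section 10.7.4 does not name treatment group either, and titles in 14.1 omit strata for SF-36 and vital signs, although the SAP text tabulates both by pre-baseline therapy. Against that, 10.7.2 and 10.7.3 do name pre-baseline therapy and 10.7.4 does not. What remains is wording to bring into line with Protocol 13.1.1.

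**Conclusion.** The point holds as a minor one on an exploratory, descriptive endpoint. The dexamethasone factor acts on baseline only in the Chronocort arm, and no planned analysis varies it. Under the assumed doses and factors, the sign of the change can turn for a subject and within the dexamethasone stratum.

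A reader might go further and infer that the factor decides the sign of the whole-arm difference. The documents do not support that. They give no dexamethasone share, no doses and no factor other than 80. Under the assumptions in step 3 the arm difference moves by about 0.75 to 3.0 mg, and in the 28 and 26 mg illustration no sign change occurs at a 10% share of baseline equivalents. That 2 mg gap is itself a change within one 16-subject cohort, not a randomised comparison, and the factor behind the 28 mg is not stated, so it serves only for scale.

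The unclear status of the cap in Table 4 is a separate gap: it alone moves the 0.5 mg example by 10 mg. Nothing here bears on which factor or dose is right.

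**What to change.** 1. In SAP 10.7.4 and 14.1, present the hydrocortisone-equivalent change and mg-band tables by treatment group and pre-baseline stratum, in line with Protocol 13.1.1. Read any dose comparison first in the hydrocortisone-only stratum, which needs no conversion.
2. Repeat the tables pooled over strata for a range of dexamethasone and prednisone/prednisolone factors. Fix the range and its source before unblinding, and report the factor, if any, at which the arm difference changes sign.
3. State in SAP 9.2.3 that the cap in Table 4 is a starting-dose rule, and say whether it applies to baseline equivalents in the analysis.

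This changes SAP wording and adds a few tables. It needs no new data and alters no dosing rule. The cost is a possibly less favourable statement about dose.
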